**Project Methods:** We will conduct a three-armed randomized trial of patient rewards for losing one pound per week over 16 weeks. The three treatment groups will receive financial rewards, non-financial rewards, or no rewards. We hypothesize that: 1) patients who receive non-financial rewards for weight loss over 16 weeks will have greater weight loss at 32 weeks than patients who do not receive rewards; 2) patients who receive non-financial rewards for weight loss over 16 weeks will experience weight loss at 16 weeks that is not inferior to the weight loss of patients who receive financial rewards; and 3) weight regain will be greater among patients who received financial rewards compared to patients who received non-financial rewards or no rewards. We will also conduct post-intervention qualitative interviews and perform a cost analysis.

## List of Abbreviations

**VA** = U.S. Department of Veterans Affairs

**CM** = Contingency management

**VAPSHCS** = VA Puget Sound Health Care System

**SMI** = Serious Mental Illness

**MOVE** (and variations of) = MOVE is not an acronym. MOVE is the VA Weight Management Program

**ERIC**= Epidemiologic Research and Information Center

**DMAP**= Data Management Access Plan

**REBS**= Regulation of Eating Behavior Survey

**NHANES** = National Health and Nutrition Examination Survey

**NHIS** = National Health Interview Survey

**SHEP**= Survey of Health Experiences of Patients

**TFEQ** = Three Factor Eating Questionnaire

**CDW** = Corporate Data Warehouse

**VSSC** = VHA Support Service Center

**CPRS**= Computerized Patient Record System

## 2.0 Introduction

Obesity and overweight are major health problems for Veterans. An estimated 37% of Veterans are overweight, and 38% are obese. Veterans who are overweight or obese have higher rates of hypertension and diabetes, and are more likely to report being in poor health. Weight loss is associated with reduced rates of morbidity and mortality. In response to the obesity epidemic, the VA created the MOVE! program. MOVE! offers a set of tools, resources, and guidance for weight management and is available to Veterans through a variety of formats, including individual and group meetings, telephone and web-based coaching. However, in a 2012 study, [name] et al found that less than 5% of Veterans who were eligible for MOVE! participated in at least one MOVE! related visit. Consequently, MOVE! is not meeting the needs of the great majority of eligible Veterans. VA National Center for Health Promotion and Disease Prevention is responding by adding more technology-based tools, but other options, including patient rewards for weight loss, should also be explored.

Recent research in behavioral economics suggests that a patient reward program for weight loss may be an effective option for Veterans. Behavioral economists argue that our chronic inability to lose weight may be explained by present bias, which is a tendency to value small immediate rewards over large, future rewards. The immediate satisfaction of consuming an unhealthy but desirable food is a relatively powerful reward compared to the distant satisfaction associated with improved health later in life that healthier diet and exercise choices bring. Individuals are also more motivated to engage in behaviors that yield concrete rewards rather than less tangible ones; reducing the probability of a myocardial infarction in the future may be too intangible to motivate present health behavior.

Patient reward programs may help to overcome present bias by providing patients with a timely, tangible reward for achieving a health-related goal. There is a growing body of evidence suggesting that rewards work for some health behaviors, including smoking, medication adherence, vaccinations and screening. Rewards are especially effective among lower-income patients, who are common in the VA population. There has been robust success using rewards for treatment of substance abuse, where it is referred to as contingency management (CM). CM has been widely implemented in addiction treatment clinics across the VA.

Financial rewards for weight loss are also effective. Several meta analyses and systematic reviews have studied the variety of forms of financial rewards, designed to make use of common decision errors. Group-based payments allow individuals who achieve a weight loss goal to share the reward of individuals in their group who failed to meet the goal, which takes advantage of our tendency to assume that we are each better than average. Lotteries take advantage of our tendency to over-estimate the probability of rare events. Deposit contracts, in which a participant forfeits their own money if they do not reach a target weight, takes advantage of loss aversion, whereby a loss decreases our perceived wellbeing by more than similar sized gain increases wellbeing. Across these various interventions, there is consistent evidence that rewards help people to lose weight while they are being given rewards, but there is little evidence that rewards lead to sustained weight loss after rewards were removed. Except for two recent trials, patients who were given rewards regained weight, such that the weight loss at follow-up was not statistically different from usual care. Thus, the key question for incentivizing weight loss is not only how to get patients to lose weight, but also how to structure the rewards so that patients maintain the weight loss after rewards are removed.

Summaries of three relevant randomized controlled trials of financial rewards for weight loss are shown in Table 1. These studies serve as a model for the proposed study; we will adhere very closely to the procedures used in these highly-respected trials, and collect and present data so that results are easily compared. We focus on these trials because the results largely support the findings of systematic analyses and meta-analyses of rewards for weight loss, and two of the studies were conducted at the VA. Two observations regarding these studies are noteworthy. First, each study found significant weight loss during the incentivized period, despite differences in the populations studied, and form and duration of the reward. The study published in JAMA had especially impressive results with half of the reward group meeting the target weight loss. Second, each study found weight regain after the financial reward stopped; however, the regain in the study published in Annals (2013) was only 3.2 lbs. in the group reward arm, resulting in a 7.5 lbs. mean weight loss that was statistically significantly different from usual care. Weight regain in the lottery arm of the JAMA (2008) study was only 3.9 lbs., which resulted in a statistically significant 9.2 lb. decrease in weight compared to baseline, although not compared to usual care. Thus, while few trials have sustained weight loss

after the reward period, we do not have far to go. The key is to design the reward with a specific emphasis on minimizing regain after the rewards are removed.

**Table 1. Three model studies of financial rewards for weight loss, and the proposed study**

Study characteristics	JAMA (2008) 	JGIM (2011) 	Annals (2013) 	Proposed study
Setting	Philadelphia VAMC (95% male)	Philadelphia VAMC (83% male)	Employees of Children's Hospital (89% female)	Seattle VAMC
Weight loss goal	1 lb./week	1 lb./week	1 lb./week	1 lb./week
Trial arms (participants per arm)	Usual care (n=19) Lottery: expected value ~\$90/month; (n=19) Deposit contract: max \$75/month (n=19)	Usual care (n=22) Deposit contract: max \$84/month (n=44)	Usual care (n=35) Individual: \$100/month (n=35) Group: \$500/month split among 5 patients (n=35)	Usual care (n=80) Financial lottery (n=100): expected value \$100/month; Non-financial raffle (n=100): expected value ~\$100/month.
Duration of rewards/total follow-up	16 weeks/28 weeks	32 weeks/68 weeks	24 weeks/36 weeks	16 weeks/32 weeks
Weight change at termination of rewards (lbs.)	Usual care: -2.9 Lottery: -13.1* Deposit contract: - 14.0*	Usual care: -1.2 Deposit contract: - 8.6*	Usual care: -1.1 Individual: -3.7 Group: -10.6*	Min detectable difference Usual care: -1.6 Lottery: -8.1 Raffle : -8.1
Weight change at follow-up (lbs.)	Usual care: -4.4 Lottery: -9.2 Deposit contract: - 6.2	Usual care: -0.3 Deposit contract: - 1.2	Usual care: -0.9 Individual: -1.8 Group: -7.5*	Min detectable difference Lottery: -3.1 Raffle : -8.1

Our target population for this study is overweight or obese Veterans, ages 18-69. Please see section 5.4 for additional information on our inclusion/exclusion criteria.

### 3.0 Objectives

The proposed study is based on the hypothesis that the regain found in prior reward studies was due in part to their use of financial rewards, and financial rewards may make patients especially susceptible to regain. Experiments in behavioral economics have found that when participants were provided financial rewards for performing a task, their behavior toward the task was defined by reciprocity—the effort the participants gave was proportional to the amount of money that they were given. When participants were given non-financial rewards, they exhibited no reciprocity—the effort was consistently high and did not vary with the quantity of the non-financial reward. These findings have been confirmed in field studies, and experiments using functional MRIs: money as a reward makes us think and behave differently. By using financial rewards, prior trials may have invoked money-market norms of reciprocity, such that patients' efforts toward weight loss were high when rewards were offered, and reduced when they were discontinued. We hypothesize that non-financial rewards, such as tickets to a Seattle Mariners baseball game, will not invoke reciprocity or the consequent weight regain. We also hypothesize that the affective or emotional characteristics of non-financial rewards can make them more powerful than financial rewards. A patient's thoughts about receiving a non-financial reward, such as tickets to baseball game, can create a positive emotional reaction that can be more salient than the cash value of the reward.

The goal of this study is to test, through a randomized trial, the effectiveness of providing obese Veterans with financial or non-financial rewards for losing 1 lb. per week over 16 weeks. The primary outcome is weight loss at 32 weeks—16 weeks after the discontinuation of the rewards. Secondary outcomes include weight loss at 16 weeks and 12 months. The specific aims are outlined below.

#### **Aim 1. Conduct a 3-armed randomized trial of patient rewards for losing 1 lb. per week over 16 weeks.**

The 3 treatment groups will receive financial rewards, non-financial rewards, and no reward (usual care).

- Hypothesis 1a: Patients who receive non-financial or financial rewards for weight loss over 16 weeks will have greater weight loss at 32 weeks than Veterans who do not receive rewards.

- Hypothesis 1b: Patients who receive non-financial rewards for weight loss over 16 weeks will experience weight loss at 16 weeks that is not inferior to the weight loss of Veterans who receive financial rewards.
- Hypothesis 1c: Weight regain between week 16 and the 32-week and 12-month follow-up, respectively, will be greater among Veterans who received financial rewards compared to Veterans who received non-financial rewards or no rewards.

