### 5.6.a. Data Analysis

All data will be analyzed at VA Puget Sound Health Care System by one of the data analysts and/or investigators.

We will use an intent to treat analysis. To test each hypothesis we will estimate an equation of the form

$\Delta Y_{it} = \beta_0 + \beta_1 Weight_{i0} + \beta_2 M_i + \beta_3 F_i + u_i$  (1) where  $\Delta Y_i$  is change in weight from baseline to follow-up time t

for patient i;  $Weight_{i0}$  is baseline weight for patient i; F is the financial rewards (arm 2); M is an indicator for assignment to non-financial rewards (arm 3); and u is a random error. To gain a small amount of efficiency we can also estimate (1) using repeated measures of change in weight from baseline to the three follow-up measures (16 weeks, 32 weeks and 12 months) using GEE models of the same form as equation (1), except with dummy variables for follow-up periods and interactions between these variables and the treatment group dummies.

Hypothesis 1a implies a test of superiority and will be assessed using two-sided tests of  $\beta_2 = 0$  for non-financial rewards, and  $\beta_3 = 0$  for financial rewards. Large positive or negative values of  $\beta_2$  and  $\beta_3$  are evidence against the null hypothesis of no difference between reward and non-reward groups.

Hypothesis 1b implies a non-inferiority test. We will reject the hypothesis that non-financial rewards are inferior to financial rewards if  $\beta_2$  is statistically significantly greater than zero (i.e., there was statistically significantly more weight loss in the non-financial reward arm than in usual care) and if  $(\beta_3 - \beta_2) < 2.5 kg$ , where  $(\beta_3 - \beta_2)$  is the adjusted difference in mean weight loss between the financial and non-financial reward arms, and 2.5 kg is half the 5 kg weight loss assumed to be clinically significant. Although there are no defined rules for choosing a range of indifference for a non-inferiority test, researchers often use half the minimum clinically significant amount. Values of  $(\beta_3 - \beta_2)$  that are statistically significantly larger than 2.5 kg are evidence against the hypothesis that non-financial rewards are not inferior to financial rewards.

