Hypothesis 1c implies a test of superiority and will be assessed using two-sided tests of  $(\beta_3 = \beta_2)$  in comparisons of weight change from week 16 to week 32 and 12 months, respectively. We will use weight change at week 16 in place of weight at baseline in equation 1, such that differences in weight regain between treatment arms will be adjusted for weight lost over weeks 1-16.

Because all secondary outcomes are continuous variables, a similar equation will be used to assess changes in secondary outcomes. These analyses explore how rewards affect constructs that are believed to mediate the effect of rewards on weight loss.

Missing weight measures will be imputed using data from patients' medical records for routine medical visits and methods developed and tested via simulation by [name] et al. These methods involve estimating longitudinal mixed-effects linear models of weight collected both through the trial and at routine clinic visits as a function of polynomials of time since enrollment, with random components for patient intercept and time, and using the predicted values from this model for any post intervention day as an estimate of what the patient's weight would have been on that day if he/she kept their follow-up appointment.

We assumed a standard deviation of 11.0 lbs. for weight loss based on the results of the JAMA (2008) and JGIM (2011) trials that were conducted in the VA and demonstrated statistically significant differences in

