weight loss at the end of the reward period. We used a two-sided alpha of 0.025 to account for the multiple comparisons between treatment groups (including for hypotheses 1b and 1c, which compare only two groups). We chose a clinically meaningful minimal detectable difference of 11 lbs. (5 kg). This was the weight loss experienced by the lifestyle management arm of the Diabetes Prevention Program randomized trial, which experienced lower rates of the incidence of diabetes. According to data from the 2012 NHANES, 11 lbs. is 5% of the average weight of 233 lbs. for obese men, and the FDA defines a weight loss drug as clinically effective if mean weight loss in the drug group is at least 5% of baseline weight. With these assumptions we would require full data on 21 patients per treatment arm at follow-up, or 28 assuming 20% loss to follow-up, in order to have 80% power to reject hypothesis 1a. In order to conduct subgroup analyses with reasonable precision, and to increase the power to detect differences in weight regain between reward groups (hypothesis 1c), we will increase enrollment to 80 patients in the no-reward arm, and we will increase the ratio of patients randomized to control versus either reward group from 1:1 to 1:1.25 for a total of 280 patients (80 usual care+100 in each reward arm). This provides a minimum detectable difference of 5.1 lbs. between treatment arms, and 4.5 lbs. if the reward arms are combined. In the three studies in Table 1, the average weight loss in the control groups at the end of follow-up was 1.6 lbs. Thus, we expect 80% power to detect weight loss as small as 6.7 lbs. in each reward group. At the end of the reward period, the average weight losses in the reward groups was 10 lbs. (range, 14 to 3.7) among the trials in Table 1. In the JAMA (2008) study, 50% of the reward group achieved their goal of 16 lbs. weight loss in 16 weeks. Thus, we have the power to detect achievable and clinically important weight losses across treatment arms.

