With 100 patients per reward arm, the minimum detectable difference for hypotheses 1b and 1c is 4.8 lbs. We will have power of 0.94 for the one-sided test of hypothesis 1b (non-financial rewards are not inferior to financial rewards). The power for hypothesis 1c (regain is lower in the non-financial compared to financial reward arm) depends on expectations of regain. We extrapolated weight regain from the trials in Table 1 in two ways: a) by assuming the weekly weight regain between the end of rewards and the last measurement continued; and b) by using data from a systematic review that found that in randomized trials of lifestyle changes for weight loss with a one year follow-up, the mean weight loss at one year was about half the weight loss achieved at 6 months. (See 2.0 Introduction for details.) We estimate that the weight regain by 12 months in the financial reward arms would be around 7.2 lbs. Thus, in order to have 80% power to reject hypothesis 1c, regain in the non-financial reward arm would need to be at most 2.4 lbs. (i.e.,  $7.2-4.8=2.4$  lbs.). The power for subgroup analyses will be limited. Simulations suggest our study sample would need to increase four fold to detect an interaction between female and treatment arm with the same power as the main analysis. We will interpret the subgroup results as exploratory, although we note that the proposed study will enroll 5 times as many female Veterans (n=70) as were enrolled in the JAMA (2008) (n=3) and JGIM (2011) (n=11) trials, combined, and more than the total enrollment of either of those trials.

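### Non-inferiority hypothesis 1b rests on intent to treat alone; without a supportive engaged-set analysis, a success can be claimed only for offering rewards, not for participants who engage with them.

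*Combined protocol and SAP*

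**What the plan says.** Under 3.0 Objectives, Aim 1, hypothesis 1b states that patients given non-financial rewards "will experience weight loss at 16 weeks that is not inferior to the weight loss of Veterans who receive financial rewards". Section 5.6.a Data Analysis opens with "We will use an intent to treat analysis" and applies one regression form to all hypotheses. It then gives 1b a two-part rule. First, the non-financial arm must beat usual care: "there was statistically significantly more weight loss in the non-financial reward arm than in usual care". Second, the adjusted difference between the reward arms must lie below the margin, where "2.5 kg is half the 5 kg weight loss assumed to be clinically significant".

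The planning figures in the same section are "We assumed a standard deviation of 11.0 lbs. for weight loss", "With 100 patients per reward arm, the minimum detectable difference for hypotheses 1b and 1c is 4.8 lbs" and "We will have power of 0.94 for the one-sided test of hypothesis 1b". On alpha it says "We used a two-sided alpha of 0.025 to account for the multiple comparisons between treatment groups (including for hypotheses 1b and 1c", and the sentence goes on to note that these two hypotheses compare only two groups.

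No per-protocol, completer, adherence-based or other sensitivity analysis for 1b appears anywhere. Section 6.1 collects compliance data monthly, but the analysis section does not use them.

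**The concern.** In a superiority test, participants who drop out of the intervention usually dilute the effect and make a claim harder. In a non-inferiority test the same dilution can help the claim, because it moves the two active arms closer together.

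The plan foresees ways for a participant to remain in the analysis without being exposed to the cash-versus-goods contrast up to week 16:

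- missed weekly entries (5.1.a, 5.7.b);
- active withdrawal with a week-16 weight still sought (5.7.a);
- removal of rewards in both reward arms once the remaining goal would need more than 4 lb a week (5.1.a).

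If 1b succeeds, a reader will want to know whether goods work about as well as cash for people who take part, or whether many in both arms had stopped taking part. As planned, the trial reports nothing that would separate the two.

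**Working it through.** **Inputs from the documents.** SD 11 lb; margin 2.5 kg, taken as 5.5 lb; 100 per reward arm and 80 in usual care (5.6.a). Table 1 plans a 16-week change of -1.6 lb in usual care and -8.1 lb in each reward arm, so the planned reward effect is 8.1 - 1.6 = 6.5 lb.

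**Assumptions.** The documents give no disengagement rate. The 20% in 5.6.a is loss to follow-up, used there only to go from 21 to 28 per arm. I therefore use a range for d, the share disengaged in each reward arm, and assume no reward effect in those participants. I read the margin rule as a one-sided test at 0.025, because that reading reproduces the plan's power with the stated 100 per arm.

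**Step 1: the plan's own figure.** SE = 11 × √(2/100) = 1.556 lb. With no true difference, power = Φ(5.5/1.556 - 1.960) = Φ(1.576) = 0.942. The stated 0.94 is reproduced, with no allowance for loss. Variants:

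| Evaluable per arm | One-sided 0.025 | One-sided 0.0125 |
|---|---|---|
| 100 | 0.942 | 0.902 |
| 80 | 0.885 | 0.821 |

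The 0.0125 column is half of the stated two-sided 0.025.

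**Step 2: similar disengagement in both arms.** Let the true deficit among engaged participants equal the margin. The intent-to-treat difference is (1 - d) × 5.5, and the chance of passing the margin test is Φ(d × 5.5/1.556 - 1.960).

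| d | Intent-to-treat difference (lb) | Chance of passing |
|---|---|---|
| 0% | 5.50 | 2.5% |
| 10% | 4.95 | 5.4% |
| 20% | 4.40 | 10.5% |
| 30% | 3.85 | 18.4% |
| 40% | 3.30 | 29.3% |

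At one-sided 0.0125 the 20% row becomes 6.2%.

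**Step 3: add the beats-usual-care condition.** This comparison has SE = 11 × √(1/100 + 1/80) = 1.65 lb. Its estimate shares the non-financial arm with the margin test, giving a correlation of (121/100)/(1.556 × 1.65) = 0.47. Testing it at two-sided 0.025 and taking the bivariate normal probability at d = 20%:

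| Non-financial effect among engaged (lb) | Chance that both conditions are met |
|---|---|
| 6.5 (planned) | 10.2% |
| 4 | 7.5% |
| 2 | 3.2% |
| 0 | 0.6% |

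**Step 4: unequal disengagement.** Take engaged effects of 6.5 lb (non-financial) and 6.5 + 5.5 = 12 lb (financial), margin test only.

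- 30% disengaged in the non-financial arm, 10% in the financial arm: difference = 0.9 × 12 - 0.7 × 6.5 = 6.25 lb; chance of passing 0.7%.
- The reverse: 0.7 × 12 - 0.9 × 6.5 = 2.55 lb; chance of passing 47%.

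**Step 5: could an engaged set mislead too?** Simulation with a true 5.5 lb deficit in everyone and 20% not reporting overall, where the tendency to report correlates with weight loss. At a correlation of 0.3 the engaged-set difference is 5.3 lb and the margin test passes 3.2% of the time; at 0.5 the figures are 4.9 lb and 5.3%.

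**The case against.** The strongest reply concerns the target. Section 3.0 sets the goal as the effectiveness of providing rewards, which is a question about the offer. For that question the 4.4 lb difference at 20% disengagement is the true effect. It lies inside the margin, so declaring non-inferiority is correct. This stands. A reader might infer that intent to treat is the wrong analysis for 1b, or that the trial has a 10% type I error. The documents support neither: the 10.5% is an error rate only for the question about engaged participants. Nor does the word receive in 1b settle the target, since 1a and 1c use it too and Aim 1 uses it for the groups as assigned.

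Three further points stand. The beats-usual-care condition protects well when the non-financial reward is weak, though hardly at the planned effect (step 3). The direction of the shift is not guaranteed (step 4). Zero difference in every disengaged participant is an extreme case, because withdrawers keep what they have already earned and are asked back for the week-16 weight.

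One might also want the margin to be met in an engaged set before non-inferiority can be declared. That goes too far. Portal entries trigger goal feedback and rewards depend on being on target, so people who are failing have a reason to stop entering weights. A set defined by reporting may therefore be selected on weight loss and can itself be too lenient (step 5).

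Finally, 1b concerns week 16, a secondary outcome. None of this removes the gap: the plan has no analysis that shows how much engagement mattered.

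**Conclusion.** The concern holds in a limited form. Intent to treat is a sound decision analysis for the offer of rewards, but standing alone it cannot support a statement about participants who engage with them. For that second question, the chance of passing the margin test with a deficit equal to the margin is about 5%, 10% and 18% at 10%, 20% and 30% disengagement, against 2.5%. These figures rest on similar disengagement in both arms, no cash-versus-goods difference among the disengaged, SD 11 lb and 100 per arm at one-sided 0.025. The disengagement range is assumed. With unequal disengagement the chance can be as low as 0.7% or as high as 47% in the cases examined. Separately, the power of 0.94 holds only with 100 evaluable per arm at one-sided 0.025.

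**What to change.** In 5.6.a, keep intent to treat as the decision analysis for 1b and add the following.

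- Pre-specify a supportive analysis with the same margin test, in reward-arm participants who kept entering weekly portal weights (for example at least 12 of 16) and who have an observed week-16 weight. Say whether weights reported at phone visits count as observed. Asking for an observed weight also avoids the imputation model, which lists no treatment-arm term and so may draw the two arms together.
- Report engagement by arm, so that the reader can judge the likely direction of any shift.
- Acknowledge that the set is formed after randomisation and may be selected on weight loss.
- State in advance that if the margin is met by intent to treat but not in this set, the 1b claim is limited to the offer of rewards.
- State that the 0.94 power assumes one-sided 0.025 and 100 evaluable per arm, and that with 80 evaluable it is about 0.89, or 0.82 at one-sided 0.0125.

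The cost is one extra analysis on data already collected, a less favourable stated power, and a non-randomised comparison that needs cautious reading.
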